## 7.4.4 Removal of Subjects From Therapy or Assessments

Although the importance of completing the entire clinical trial will be explained to the subjects, any subject is free to discontinue his/her participation in the study at any time and for whatever reason, specified or unspecified, and without any prejudice. No constraints are to be imposed on the subject, and when appropriate, a subject may be treated with other conventional therapy when clinically indicated. Investigators or the sponsor can also withdraw subjects from the clinical trial if deemed to be necessary.

Subjects may stop study drug for any of the following reasons:

- Subject consent withdrawal
- · Use of non-permitted concurrent therapy
- Non-compliance with the study drug or study schedule
- Lost to follow-up
- Occurrence of AEs not compatible with the continuation of subject participation in the study, in the investigator's opinion, or unacceptable to the subject to continue
- Serious immediate-type allergic manifestations including anaphylactic reaction
- Pregnancy
- Use of systemic rescue therapy during the run-in period through the Week 12 visit (last study drug injection), unless otherwise specified in Table 8 of Section 7.5.8.2.
- Investigator request
- · Intercurrent illness
- Diagnosis of a malignancy (except curatively treated in situ cervical carcinoma or basal cell carcinoma)
- Any opportunistic infection (such as active TB and other infections whose nature or course suggest an immune-compromised status)
- Sponsor request
- Treatment failure

The reason(s) for withdrawal will be documented in the case report form (CRF). Subjects who have been enrolled and treated will not be replaced by another subject.

CONFIDENTIAL Page 45 of 99

Subjects who prematurely discontinue study drug will be encouraged to complete the scheduled study visits.

When a subject discontinues study drug, he/she will be fully assessed whenever possible. Subjects discontinuing study drug before the Week 16 visit should attend an early termination visit and a follow-up/final visit 12 weeks after the last study drug injection for safety follow-up.

Reasonable efforts will be made to contact subjects who are lost to follow-up. These efforts must be documented in the subject's file.

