3.6. Treatment Assignment & Blinding

Eligible subjects will be sequentially assigned to receive treatment with open-label nemolizumab, based on the time of enrollment.

Although some subjects will be screened and assigned a subject identification number (SIN), they may not be eligible for enrollment/treatment, and thus they will not be enrolled in the study.

Dose modification of the study drug will not be permitted during the clinical trial.

Any inadvertent dose modification(s) should be reported to the sponsor/CRO.

In the event of a missed dose (ie, temporary discontinuation of the study drug), it will be documented in the case report form (CRF) that the drug has not been administered at the study visit, together with the reason (eg, for safety). Subjects will be asked to return to the study centers for all remaining visits and complete all study assessments and procedures.

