3.7. Administration of Study Medication

Dosing frequency is scheduled for every 4 weeks, based on the baseline/Day 1 visit date. If a study visit occurs outside the visit window, study drug can be administered with a minimum of 3 weeks since the last injection. Future visits should be scheduled within the required windows based on the baseline/Day 1 visit date, while maintaining the minimum 3-week interval between 2 injections.

As described in Table 1, Nemolizumab (CD14152) will be administered as a subcutaneous injection, with a loading dose of 60 mg on Day 1, followed by injections of 30 mg every 4 weeks for 12 weeks.

Table 1 Dosing Scheme

Group	Dose on Day 1	Dose at Weeks 4, 8 and 12
1	60 mg	30 mg

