5.3. Pharmacokinetic Analysis Population

The Pharmacokinetic (PK) analysis population will include all subjects in the safety population who provide at least one post-baseline evaluable drug concentration value. PK endpoints will be analyzed using the PK population. Subjects will be analyzed according to the treatment actually received.

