6.1. General Methods

This section describes analytical analysis issues that relate to all or some of the analytic analysis sections that follow. It describes general guidelines for analysis as well as the following items:

- SAS version 9.4 or higher will be used.
- CCI will be responsible for reporting the demographic, safety, and efficacy data including listings of the administration information for collection of PK and PD samples.
- Unless otherwise specified, summaries will be presented by visit.
- The total number of subjects in the treatment group (N) will be used as the denominator for percentage calculations, unless stated otherwise in the table shell.
- Continuous variables will be summarized using the number of observations (n), mean, standard deviation (SD), median, minimum, and maximum. Categorical variables will be summarized using number of observations (n) and percentages of subjects.
- Subject data listings will be presented with the ITT population for efficacy assessments, with the Safety Population for safety assessments and with the PK population for PK assessments, unless stated otherwise.
- In general, the listings will be sorted by subject number, and assessment date (and time) if applicable.
- Multiple assessments at a given time point (repeat, and unscheduled) will not be included in summary tables unless specified otherwise, but will be included in the listings.

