6.6. Analysis Visit Window

Efficacy by-visit summaries will use the analysis visit. Unscheduled and early termination visits will be windowed based on the following analysis visit window. If multiple measurements are taken within the same window, the one taken closest to the target study day will be used for the analysis. If there are multiple measurements with same difference from target day, the later assessment should be used for the analysis.

		Visit	Window
Analysis Visit	Target Study Day	EASI, IGA, BSA, SCORAD	DLQI/cDLQI
Baseline	1	<=1	<=1
Week 1-2	10	2 to 19	NA
Week 4	29	20 to 42	NA
Week 8	57	43 to 71	NA
Week 12	85	72 to 99	NA
Week 16	113	100 to 141	100 to 141
Week 24 Follow-up	169	> 141	> 141

Daily diary efficacy data (pruritus and sleep disturbance NRS) will be classified into analysis visits as follows considering the data during the 7 days immediately preceding each scheduled visit.

This document is confidential.

SAP Version: Final Version 3.0, 21-Sep-2020

Controlled Document ID: 3903A.01, Effective Date 29-Oct-2018

Filing requirements: TMF

Sponsor: Galderma Research & Development, LLC; Protocol No.: RD.06.SPR.116912, Version 6.0

Analysis Visit	Target Study Day	Diary Data Window
Baseline	1	-7 to -1
Week 1-2	10	3 to 9
Week 4	29	22 to 28
Week 8	57	50 to 56
Week 12	85	78 to 84
Week 16	113	106 to 112
Week 24 Follow-up	169	162 to 168

Daily topical AD medication used data will be classified into visit intervals as follows.

Analysis Visit Interval	Target Study Day	Diary Data Window
Baseline to Week 1-2	10	1 to 9
Week 1-2 to Week 4	29	10 to 28
Week 4 to Week 8	57	29 to 56
Week 8 to Week 12	85	57 to 84
Week 12 to Week 16	113	85 to 112
Week 16 to Week 24 follow-up	169	113 to 168

Safety and pharmacokinetics data will not be windowed for by-visit summary. i.e., scheduled visit data will be used for analysis.

7. Demographic, Other Baseline Characteristics and Medication

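### The by-visit concentration summary and the ADA trough comparison have no rule on doses received or time since dose, so off-schedule samples are averaged with regular troughs

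*SAP*

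**What the plan says.** **How samples enter the tables.** SAP 6.6 states "Safety and pharmacokinetics data will not be windowed for by-visit summary" and takes the samples of the scheduled visits as they stand. SAP 9.1 summarises serum concentrations by visit from baseline to Week 24; the only values it removes are those below the limit of quantification (BLQ). SAP 6.1 adds that "Multiple assessments at a given time point (repeat, and unscheduled) will not be included in summary tables unless specified otherwise". SAP 9.3 compares the average observed trough between ADA-positive and ADA-negative samples by ANOVA.

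**Who is eligible.** The PK population takes safety-population subjects "who provide at least one post-baseline evaluable drug concentration value". The term evaluable is not defined, and it selects subjects, not samples.

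**How off-schedule samples arise.**
- After a missed dose, SAP 3.6 says "Subjects will be asked to return to the study centers for all remaining visits and complete all study assessments and procedures"; Protocol 7.5.7 says the same.
- After stopping drug, Protocol 7.4.4 says "Subjects who prematurely discontinue study drug will be encouraged to complete the scheduled study visits".
- When a visit falls outside its window, SAP 3.7 says "study drug can be administered with a minimum of 3 weeks since the last injection".
- Protocol 7.2 allows ±3 days at Weeks 4 and 8 and ±5 days at Weeks 12 and 16.

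**How the results are used.** Observed concentrations by visit are the first PK item among the primary endpoints (Protocol 6.2.1, SAP 4.1). Table 14.2.3.1, which reports them, is the only PK summary table that SAP 18 marks for the interim. That interim asks whether adolescent PK and safety resemble adult data (SAP 13).

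**The concern.** A trough mean can be interpreted only if its samples share the same dosing history and roughly the same time since dose. Here a scheduled Week 8 sample taken eight weeks after the last injection counts the same as one taken four weeks after it. Nothing in SAP 6.1, 6.6, 9.1 or 9.3 separates the two.

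At stake is the observed adolescent-to-adult comparison at the interim, with about 10 subjects, where one such sample changes the mean and widens the spread. In the ADA comparison, a low value caused by a missed dose would be attributed to whichever ADA group the sample falls in.

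**Working it through.** The plan gives no figure to reproduce: the sample size of 20 is not derived from stated inputs. The check is an illustration of size.

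**Inputs**
- Doses of 60 mg at Day 1 and 30 mg at Weeks 4, 8 and 12 (Protocol Table 6).
- Half-life: Protocol 7.3.1 equates 12 weeks with 5 half-lives, so 84/5 = 16.8 days. The range of 14 to 21 days is my assumption.
- One compartment (Protocol 8.2.2), linear, instant absorption. An assumed absorption rate of 0.3 per day hardly changes the results.
- The affected subject is otherwise average.

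**Regular troughs.** The fraction left after 28 days is f = 2^(−28/16.8) = 0.315. In dose units:
- Week 4: 60 × 0.315 = 18.90
- Week 8: (18.90 + 30) × 0.315 = 15.40
- Week 12: (15.40 + 30) × 0.315 = 14.30
- Week 16: (14.30 + 30) × 0.315 = 13.95

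**Off-schedule samples**
- Week 4 dose missed, Week 8 sample: 18.90 × 0.315 = 5.95; 5.95/15.40 = 0.386.
- Week 8 dose missed, Week 12 sample: 15.40 × 0.315 = 4.85; 4.85/14.30 = 0.339.
- Stopped after the Week 4 dose, Week 16 sample: 15.40 × 0.315² = 1.53; 1.53/13.95 = 0.110.
- Week 8 dose given 7 days late, Week 12 sample on time (21 days after dose): 60 × 2^(−84/16.8) + 30 × 2^(−56/16.8) + 30 × 2^(−21/16.8) = 1.88 + 2.98 + 12.61 = 17.47; 17.47/14.30 = 1.22.

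**Shift in the visit mean from one affected subject.** With sample ratio r, the arithmetic shift is (r − 1)/N and the geometric shift is r^(1/N) − 1. Ranges in brackets are for half-lives of 21 and 14 days. N = 10 is used only for the Week 8 interim; Weeks 12 and 16 are taken at the planned N = 20.

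| Case | N | Arithmetic | Geometric |
|---|---|---|---|
| Missed Week 4 dose, Week 8 | 10 | −6.1% (−5.6 to −6.7) | −9.1% (−7.8 to −10.4) |
| Missed Week 8 dose, Week 12 | 20 | −3.3% (−2.9 to −3.6) | −5.3% (−4.3 to −6.3) |
| Stopped after Week 4 dose, Week 16 | 20 | −4.5% (−4.2 to −4.7) | −10.5% (−8.5 to −12.5) |
| 21-day interval, Week 12 | 20 | +1.1% (+0.8 to +1.5) | not computed |

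**Would a study-day window solve it?** No. The efficacy window for Week 12 is Days 72 to 99, so a Day 85 sample after a missed Week 8 dose sits exactly on target. Timing inside the protocol's own visit windows also matters: dose on Day 54 and sample on Day 90 (36 days apart) gives −25%; dose on Day 60 and sample on Day 81 (21 days apart) gives +28%.

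**Against sampling error.** The documents give no coefficient of variation. For an assumed 30 to 60%, the standard error CV/√N is 9.5 to 19.0% at N = 10 and 6.7 to 13.4% at N = 20.

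**The case against.** The strongest reply is that the results that matter most are protected. Protocol 9.4.2 treats the model-based parameters as the primary PK endpoints. SAP 9.2 derives them from each subject's dosing history and measured concentrations, and an interim model analysis is planned as well. This stands. A reader might infer that the whole primary PK endpoint is biased; the documents do not support that, because only its observed-concentration part is exposed.

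A reader might also infer that the lack of windowing is the cause. It is not, as the working shows. Leaving PK data unwindowed in fact keeps early-termination samples from being mapped into visits, and repeat and unscheduled samples stay out of the tables, so it would be wrong to say that every sample enters.

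Nor is a consistent downward bias established. Short intervals act upward. Excluding BLQ values can hide part of any downward shift, since a value at 0.11 of expected might fall below the limit, which the documents do not give. No missed-dose rate is stated, and dosing is done by site staff with only four doses, so deviations may be few. One subject's arithmetic shift is below the standard error under the assumed CVs.

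Individual profiles and the listings of concentrations and drug administration are marked for the interim, so a careful reader could spot an odd subject. Table 14.2.3.1 is also titled as concentrations, not troughs. Both points are fair, but spotting a subject afterwards does not replace a rule set in advance, and SAP 9.3 does call its variable a trough. A separate PK modeling plan, not supplied here, may set exclusions for the model and the non-compartmental analysis (NCA). SAP 9.1 does not refer to it for the concentration table.

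**Conclusion.** The gap is real but limited. The by-visit concentration summary and the ADA trough ANOVA lack a dose-received and time-since-dose rule, although the documents provide for subjects to be sampled after missed doses, after stopping and at irregular intervals. The population PK parameters are unaffected.

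One affected subject shifts a geometric mean by about 9% at the Week 8 interim, and by about 5 to 10% at Weeks 12 and 16 with N = 20. Arithmetic shifts are smaller, about 6% and 3 to 4.5%. These sizes rest on the half-life implied by the protocol, a linear one-compartment model and one otherwise average subject. The net direction and the number of affected subjects are unknown. The change should be made because it is cheap and alters a reported result, but the model-based conclusions do not depend on it.

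**What to change.** In SAP 5.3, 9.1 and 9.3:

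- Define evaluable at sample level. Derive a flag from the injection and sample times, including missed injections, that Protocol 8.2.1 already records: all scheduled doses so far received, and days since the last dose within a pre-set range around 28. With earlier doses on time and a 16.8-day half-life, ±3 days keeps a trough within 2^(±3/16.8), or 0.88 to 1.13 of expected; ±5 days gives 0.81 to 1.23.
- For the trough visits (Weeks 4, 8, 12 and 16) in Table 14.2.3.1 and Figure 14.2.3.5, and for the ADA ANOVA, use conforming samples and show the all-sample version as sensitivity.
- Keep the Weeks 1-2 and Week 24 summaries. They belong to the endpoint, and every NCA AUC uses the Weeks 1-2 sample, so a blanket pre-dose restriction would do harm.
- Flag, but do not drop, NCA AUCs from subjects with dosing deviations; a lower AUC after a missed dose is that subject's actual exposure.
- Mark the flag in Listing 16.2.5.4 and keep all samples in the population PK analysis.

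The cost is SAP wording, one derived variable and a sensitivity version of the affected outputs. The drawback is a slightly smaller n at some visits.

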7.1. Subject Disposition and Withdrawals

All subjects who provide informed consent will be accounted for in this study.

Summary of accounting of subjects who enter the study will be provided.

Subject disposition will be summarized for all subjects. Subjects screened, screen failed with reason for screen failure, treated, completed the study, discontinued treatment with reason for discontinuation of treatment, and discontinued the study along with reason for discontinuation from the study will be summarized using number and percent of subjects. Percentage of screen failure reason will be based on the number of screen failures. Percentage of subjects treated, completed or discontinued will be based on the number of subjects in ITT population.

Subject disposition will also be summarized by site on the ITT population excluding summaries of subjects screened and screen failures.

Subjects in each analysis population (ITT, Safety, PK population) will be summarized separately.

Subject study completion status, study drug completion status, subjects not meeting eligibility criteria, subjects in analysis population will be listed.

In addition, time (days since the first dose of study drug) to permanent discontinuation of study drug by reason for discontinuation will be displayed graphically in subjects having permanently discontinued from the study drug.

7.2. Protocol Deviations

Major protocol deviation will be summarized on the ITT population, and also summarized by site.

All protocol deviations (major and minor) will be listed on the ITT population.

7.3. Demographic and Other Baseline Characteristics

Age (years), height (cm) at screening, weight (kg) at baseline, weight (kg) by age group (12-14 years, 15-17 years), and BMI (kg/m²) will be summarized using summary statistics for continuous variables. BMI will be calculated using height at screening and weight at baseline.

If height is recorded in inches (in) then height will be summarized in cm by the following:

Height (cm) = Height (in) * 2.54

If weight is recorded in pounds (lbs) then weight will be summarized in kilograms (kg) by the following:

Weight (kg) = Weight (lbs) * 0.4536

Age group (12-14 years, 15-17 years), sex, race, ethnicity will be summarized using the summary statistics for categorical variables. Summary statistics for demographic and baseline characteristics will be presented for the ITT population.

In addition, baseline disease characteristics will also be summarized for EASI, IGA, BSA involvement of AD, weekly average of peak pruritus NRS, weekly average of average pruritus NRS, weekly sleep disturbance NRS, SCORAD, DLQI, cDLQI.

All demographic and baseline characteristics data will be listed on the ITT population.

7.4. Medical History

Medical history will be coded using Medical Dictionary for Regulatory Activities (MedDRA, Version 21.1).

Medical History will be summarized using the number and percent of subjects reporting each system organ class (SOC) and preferred term (PT) and sorted alphabetically by SOC and descending frequency of PT within SOC. Summary tables will be presented for ITT population.

Medical history data listings will be sorted by subject number, onset date, end date, SOC, and PT.

7.5. Medical and Surgical Procedures

Medical and surgical procedures be coded using Medical Dictionary for Regulatory Activities (MedDRA, Version 21.1).

Medical and surgical procedures will be classified as follows:

- Prior procedure: defined as procedures that started and ended before first treatment date.
- Concomitant procedure: defined as procedures started or ongoing or ended on or after first treatment date.

Prior and concomitant medical and surgical procedures will be summarized separately using the number and percent of subjects reporting each system organ class (SOC) and preferred term (PT) and sorted alphabetically by SOC and in descending frequency of PT within SOC. Summary tables will be presented for ITT population.

Prior and concomitant medical and surgical procedures listings will be provided and sorted by subject number, onset date, end date, SOC, and PT.

7.6. Medication

Medications will be classified and presented on the ITT population as follows:

- Prior medications: defined as medications that started and ended prior to the first treatment date.
- Concomitant medications: defined as medications that started or ongoing or ended on or after the first treatment date.
- Rescue Medication: only medication that directly treat AD (mainly those that are approved or are standard of care), and include topical and systemic treatments. And Rescue medications will be classified by period (treatment period, follow-up period).
 - Rescue medication during treatment period is a medication which started from the first treatment date to the date of Week 16 (for week 16 completers) or the earliest date between 4 weeks after the last study drug injection or the date of early termination (for discontinued subject).
 - Rescue medication during follow-up period is a medication which started from the date of the post end of treatment period to the date of follow up visit.
- Background topical corticosteroids (TCS): permitted background TCS used throughout the study.

If the stop date and 'ongoing' are missing then the medication will be considered as concomitant medication. If stop date is partially missing, the medication will be considered as concomitant medication unless the non-missing part of date proves it ended prior to the first treatment date.

Medications (prior, concomitant and rescue medications) will be coded using Version Sept 2018 of the World Health Organization's Drug Dictionary (WHO DD). Preferred Anatomical Therapeutic Chemical (ATC) coding will be performed. Background TCS will not be coded.

The number and percentage of subjects with prior and concomitant medications will be summarized for the ITT population by the ATC Level 4 and the preferred drug name (PT), and sorted alphabetically by ATC level term and descending frequency of PT within ATC level term.

All rescue medications and topical rescue medications (route=topical) will be summarized by period (treatment and follow-up periods) for the ITT population by the ATC Level 4 and PT.

Prior, concomitant and rescue medication summaries will be sorted alphabetically by ATC level term and sorted in descending frequency of PT within ATC level term.

Background TCS will be summarized (number and percentage) by medication name for the ITT population and sorted in descending frequency of medication.

All medications (prior and concomitant medications, rescue medications, and background TCS) will be listed on the ITT population.

8. Efficacy

All the efficacy analyses will be based on the ITT population. All efficacy variables will be summarized by visit from baseline unless specified otherwise. For efficacy analysis, unscheduled visit or ET visit data will be considered for by-visit summary.

All efficacy analysis will be performed using LOCF or Non-responder imputation (unless stated otherwise) and also performed with observed cases (OC) as sensitivity analysis (see Section 6.3 for more details). LOCF and Non-responder will be performed at all post-baseline visits up to Week 24.

In LOCF or Non-responder analyses, all efficacy data will be set to missing after rescue medication is used. In OC analyses, all data will be included even if subject has received rescue medication.

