### Rescue Therapy:

If deemed to be medically necessary by the investigator (eg, to control intolerable AD signs/symptoms), rescue therapies can be prescribed to the subjects at any time during the study except during the run-in period. Subjects receiving rescue therapies during the run-in period are not eligible to participate in the study. As a general guideline and per individual investigator judgment, rescue therapy should not be prescribed within the first 2 weeks after baseline (ie, Week 2 visit) to allow a minimum period for study drug exposure in the presence of background therapy. Rescue treatments are only treatments that directly treat AD (mainly those that are approved or are standard of care), and include topical and systemic treatments as outlined. Some rescue therapies include:

- Topical calcineurin inhibitors (TCI)
- Higher potency of TCS (class I-II according to the US classification)
- Oral corticosteroids
- Biologics (including their biosimilars)
- Systemic nonsteroidal immunosuppressants/immunomodulators
- Phototherapy

Antihistamines, sleep aids, topical and systemic antibiotics, and anti-itch creams are not considered to be rescue therapy because they do not directly treat AD.

Whenever possible, investigators should first use topical medications as rescue therapy before escalating to systemic therapies. If subjects receive topical treatments or phototherapy as rescue therapy, study drug administration should be continued unless there is a safety concern according to the investigator's judgment. If subjects receive systemic rescue therapy, the study drug administration must be permanently discontinued.

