#### 7.5.7 Dose Modification

Dose modification of the study drug will not be permitted during the clinical trial.

Any inadvertent dose modification(s) should be reported to the sponsor/CRO.

CONFIDENTIAL Page 49 of 99

In the event of a missed dose (ie, temporary discontinuation of the study drug), it will be documented in the CRF that the drug has not been administered at the study visit, together with the reason (eg, for safety). Subjects will be asked to return to the study centers for all remaining visits and complete all study assessments and procedures as described in Section 7.2.

Dosing frequency is scheduled for every 4 weeks, based on the baseline/Day 1 visit date.

Prior therapies are defined as therapies that have been stopped within the 3 months preceding the screening visit, unless relevant to the inclusion/exclusion criteria. Whenever possible, prior therapies for AD should be documented.

Concomitant therapies are defined as follows:

- · any existing therapies ongoing at the time of the screening visit,
- any changes to existing therapies (such as changes in dose, formulation or application frequency) during the course of the study, or
- any new therapies received by the subject since the screening visit.

The following 2 categories are to be considered for prior and concomitant therapies:

- Drugs/therapies include but are not limited to prescription, over-the-counter, birth control
  pills/patches/hormonal devices, vitamins, moisturizers, sunscreens, herbal
  medicines/supplements, and homeopathic preparations.
- Medical and surgical procedures (eg, phototherapy, exodontia, etc). Procedures whose sole
  purpose is diagnosis (non-therapeutic) are not included.

Prior and concomitant therapies for drugs/therapies or for medical/surgical procedures are to be recorded in the appropriate CRF. Concomitant therapies are to be recorded, reviewed, and updated at each visit. At each visit, investigators should also confirm concomitant therapies for contraception. (Contraceptive counseling should occur at screening). Any new concomitant therapy or modification of an existing therapy may be linked to an AE. A corresponding AE form should be completed to account for the change in therapy, except in some cases such as dose modification for a chronic condition, in which case the medication will be linked to an item in the subject's medical history.

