### Phototherapy

Whenever possible, investigators should first use topical medication as rescue therapy, before escalating to systemic therapies. If subjects receive topical treatments or phototherapy as rescue therapy, study drug administration should be continued unless there is a safety concern according to the investigator's judgment. If subjects receive systemic rescue therapy, the study drug administration must be permanently discontinued.

For the purpose of efficacy analysis, subjects receiving any rescue therapies will be considered as treatment failures.

Further, the use of any rescue therapies should be documented in the CRF.

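### The SAP defines rescue only as medication, so phototherapy rescue, which the protocol files as a procedure, can be missed by the rule that discards post-rescue efficacy data

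*SAP*

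**What the plan says.** **Protocol.** The synopsis and Section 7.5.8.1.2 describe rescue in terms of treatments, not drugs: "Rescue treatments are only treatments that directly treat AD (mainly those that are approved or are standard of care"). Both lists of examples end with phototherapy. Section 7.5.8.1.2 adds three things that matter here:

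- dosing goes on: "If subjects receive topical treatments or phototherapy as rescue therapy, study drug administration should be continued", barring a safety concern;
- the efficacy consequence: "subjects receiving any rescue therapies will be considered as treatment failures";
- the record: "the use of any rescue therapies should be documented in the CRF", with no form named.

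The prior and concomitant therapy text (listed as Section 7.5.8 in the table of contents, printed after the dose-modification text of 7.5.7) splits what is recorded into two categories, drugs/therapies and "Medical and surgical procedures (eg, phototherapy, exodontia, etc"). Phototherapy is the first example of a procedure.

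**SAP.** Section 7.6 places rescue under medications and defines it as "only medication that directly treat AD (mainly those that are approved or are standard of care), and include topical and systemic treatments". It dates rescue by the start of a medication, codes it in WHO DD, and tabulates it by ATC level. Section 7.5 codes procedures in MedDRA and gives them two classes, prior and concomitant; the latter is "Concomitant procedure: defined as procedures started or ongoing or ended on or after first treatment date". There is no rescue class for procedures. Section 8 says that in the LOCF and non-responder analyses "all efficacy data will be set to missing after rescue medication is used". Section 6.3, to which Section 8 refers for detail, states the same rule with rescue therapy as the trigger. The SAP text available does not name phototherapy, and it does not define rescue therapy.

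**The concern.** The SAP has taken over the protocol's sentence on rescue, replaced treatments by medication, and dropped the list that brought phototherapy in. The words topical and systemic do not restore it, because the protocol names phototherapy separately from both (Sections 7.3.1 and 7.5.8.1.2).

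Phototherapy treats the disease under study, and the subject normally stays on nemolizumab and keeps attending visits. If the record is not recognised as rescue, improvement after phototherapy can be counted as response on nemolizumab in EASI, IGA, BSA, SCORAD and the NRS scores, against the protocol's own failure rule. The rescue summaries could also understate how often rescue was needed. These include Table 14.1.4.3, marked for both the interim analysis and the IDMC, and Table 14.1.4.4, marked for the IDMC.

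**Working it through.** The plan has no figure to reproduce: N = 20 is stated without formal powering (SAP 3.5), and no rescue rate is given. The check is a trace through the text, followed by simple arithmetic for the size.

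**1. One phototherapy record traced through the plan**

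| Step | Source | Result for phototherapy |
|---|---|---|
| Is it rescue? | Protocol synopsis, 7.5.8.1.2 | Yes, listed |
| Does dosing continue? | Protocol 7.5.8.1.2 | Yes, barring a safety concern |
| Efficacy status | Protocol 7.5.8.1.2 | Treatment failure |
| How is it recorded? | Protocol 7.5.8 text | Medical and surgical procedure |
| SAP class of a procedure | SAP 7.5 | Prior or concomitant only |
| SAP definition of rescue | SAP 7.6 | Medication only |
| Trigger for discarding later data | SAP 6.3 | Rescue therapy, undefined in the SAP |
| Trigger for discarding later data | SAP 8 | Rescue medication, as defined in 7.6 |
| Rescue tables 14.1.4.3 and 14.1.4.4 | SAP 18 | By ATC level, so drugs only |

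A programmer who follows 7.6 and 8 to the letter gets no rescue date for this subject and keeps the later scores. A programmer who reads 6.3 together with the protocol discards them. The two readings give different results from the same data. The observed-case analysis is the same either way, since it keeps post-rescue data by design.

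**2. IGA success, non-responder analysis**

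Missing counts as failure, so the denominator is taken as all 20 subjects. If k phototherapy-rescued subjects meet IGA success at Week 16 (score 0 or 1 and at least a 2-grade improvement) and are not flagged, the rate rises by k/20:

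- k = 1: 1/20 = 5 percentage points
- k = 2: 2/20 = 10 points
- k = 3: 3/20 = 15 points

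Illustration with assumed counts: 6/20 = 30% (exact 95% CI 11.9 to 54.3) becomes 5/20 = 25% (8.7 to 49.1) once one subject is reclassified.

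**3. Continuous endpoints under LOCF**

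If the retained value differs from the carried-forward pre-rescue value by d, the mean over 20 subjects moves by d/20. For percent change in EASI, assumed differences of 20, 50 and 80 points give 20/20 = 1.0, 50/20 = 2.5 and 80/20 = 4.0 points. The sign depends on whether the subject was better or worse after phototherapy than before it.

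**4. How likely is any case?**

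With an assumed per-subject probability p of phototherapy rescue, the chance of at least one case in 20 is 1 − (1 − p)^20:

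- p = 1%: 18%
- p = 2%: 33%
- p = 5%: 64%
- p = 10%: 88%

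These rates are assumptions that span a range; none comes from the documents.

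**The case against.** The best defence is that the documents, read together, already give the right answer. SAP 6.3 is the missing-data section, Section 8 points to it, and it uses rescue therapy. The protocol says what that covers, and SAP 14 declares no departure from protocol methods. The protocol itself uses the terms loosely: Section 9.3 is headed with rescue therapy, triggers on rescue medication and ends with rescue treatment, and Appendix 2 speaks of a rescue medication while pointing to the section whose list includes phototherapy. Protocol Table 8 also prohibits phototherapy from Day 1 to Week 24 unless used as rescue, so a permitted on-study record is rescue and can be found. The CRF is not available, and it may carry a rescue page or a flag.

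Much of this stands. A reader might infer that a phototherapy-rescued subject is bound to stay in the main analyses, or that no dataset could identify one. The documents support neither: Section 6.3 points the other way, and the CRF cannot be checked. What the defence does not supply is a rule. The SAP has one rescue definition, it covers medications only, and Section 8 uses its wording.

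Three further inferences also go too far:

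- That the error always favours the drug. This is so for non-responder IGA, where an unflagged subject can only gain. Under LOCF, a subject who worsened despite phototherapy would make the retained result worse than the carried-forward one.
- That concomitant phototherapy would go unreported because Listing 16.2.4.4 is titled for prior procedures only. SAP 7.5 commits to listings of prior and concomitant procedures, and Table 14.1.3.3.2 summarises concomitant ones, including at the interim. The IDMC can also request other outputs (SAP 13).
- That the count of medication-free days in SAP 8.7 shares the fault. That endpoint counts days without topical medication. How to treat days after other rescue is a separate choice of estimand, and no change to it follows from this point.

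**Conclusion.** The SAP's rescue definition is narrower than the protocol's, and its efficacy rule is worded in two ways that need not give the same result. Followed literally, Sections 7.6 and 8 can leave a phototherapy-rescued subject's later scores as observed data in the LOCF and non-responder analyses, contrary to the protocol's failure rule, and can leave the subject out of the ATC-based rescue tables. Whether this happens depends on how the derivation is programmed, which the SAP does not settle.

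The size is 5 percentage points of non-responder IGA success per affected subject at N = 20, provided that the subject meets IGA success at Week 16. For the LOCF endpoints the shift is probably favourable to nemolizumab, but this is not guaranteed. The number of affected subjects is unknown and may be zero.

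The reach is limited. Efficacy is secondary, descriptive and single-arm. The primary PK and safety analyses are untouched, and no efficacy table is marked for the interim analysis. It should be corrected, but it does not threaten the study's main purpose.

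**What to change.** In SAP 7.6, define rescue therapy once, as rescue medications plus phototherapy recorded as a procedure with a start date on or after first treatment. Use that term and that start date in Sections 6.3 and 8, so that later efficacy data are treated as missing in the LOCF analyses and as non-response in the binary ones. Add a cross-reference in Section 7.5. Include phototherapy in the rescue tables for the treatment and follow-up periods (14.1.4.3 and 14.1.4.4) and in Listing 16.2.4.6, as a separate row because it has no ATC code. Section 8.7 needs no change.

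The cost is a few lines of SAP text and one programming condition. The protocol already requires rescue and procedures to be recorded in the CRF, so no new data are needed. Reported efficacy may be slightly less favourable.
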